5.3.2 Reasons for Withdrawal

A study subject may be discontinued from participation in the study for the following reasons:

- Any clinical adverse event (AE)
- Withdrawn Consent
- Protocol Violation (e.g., violation of any exclusion criteria)
- Lost to Follow-Up

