5.3.3 Handling of Withdrawals

If a subject is withdrawn prior to the end the study, the reason for withdrawal will be documented and entered into the eCRF and if patient is willing to return to be assessed, the End of Treatment (Day 180) assessments will be completed. Documentation of withdrawal in the source documents should include a distinction between participant withdrawal from the study medication regimen and withdrawal from the study itself. In the former case case, the study medication is stopped, but the participant, if willing, continues with study visit assessments; in the latter, study medication and study visit assessments are discontinued.

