6.3 Modification of Study Intervention/Investigational Product for a Participant

Dose increase, reduction or cessation is permitted at the discretion of the investigator. Any modification to the dosing regimen will be noted in the source document and entered into the eCRF.

The Investigator will consider a dose modification For the following combined drug levels (itraconazole + hydroxyitraconazole) at Day 14 and Day 42:

- <500ng/ml increase dose

- >5000ng/ml decrease dose

Any modification to the dosing regimen should have blood-levels re-analyzed every two weeks until the target therapeutic level is achieved (see schema below).

The Investigator will consider dose reduction and/or dose cessation for toxicity if the participant:

- Develops a study drug-related, grade 4 adverse event
- Develops a study drug-related, serious adverse event (SAE)
- Develops dose-limiting study drug-related toxicity despite dose-reduction.

6.4 Accountability and Assessment of Subject Compliance with Study Intervention/Investigational Product

Study drug accountability procedures will be performed by the clinical site. The site will maintain all product per storage guidelines highlighted in the product insert or IB. The clinical site will document receipt, dispensing, and any unused product. This documentation will be maintained throughout the conduct of the study.

Study drug compliance will be assessed at each visit (Day 7, Day 14, Day 28, Day 42, Day 84, Day 180). Subjects will bring all containers and unused medication (if applicable) to each visit. Sites will determine the total amount of product dispensed and compare it to returned product. This information will be collected on the source documents and entered into the eCRF.

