8.4 Methods and Timing for Assessing, Recording, and Analyzing Safety Parameters

8.4.1 Adverse Events

ICH E6 defines an AE as any untoward medical occurrence in a patient or clinical investigation subject administered a pharmaceutical product regardless of its causal relationship to the study treatment. An AE can therefore be any unfavorable and unintended sign (including an abnormal laboratory finding), symptom, or disease temporally associated with the use of medicinal (investigational) product. The occurrence of an AE may come to the attention of study personnel during study visits and interviews of a study recipient presenting for medical care, or upon review by a study monitor.

All AEs including local and systemic reactions not meeting the criteria for "serious adverse events" should be captured on the appropriate CRF. Information to be collected includes event description, time of onset, clinician's assessment of severity, relationship to study product (assessed only by those with the training and authority to make a diagnosis, which would include MD, PA, Nurse Practitioner, DO, or DDS), and time of resolution/stabilization of the event. All AEs occurring while on study must be documented appropriately regardless of relationship. All AEs will be followed to adequate resolution.

Any medical condition that is present at the time that the patient is screened should be considered as baseline and not reported as an AE. However, if it deteriorates at any time during the study, it should be recorded as an AE.

All AEs must be graded for severity and relationship to study product.

FDA defines an AE as any untoward medical occurrence associated with the use of a drug in humans, whether or not considered drug related.

Severity of Event: All AEs will be assessed by the clinician using a protocol defined grading system. For events not included in the protocol defined grading system, than the following guidelines will be used to quantify intensity.

- Mild: events require minimal or no treatment and do not interfere with the patient's daily activities.
- Moderate: events result in a low level of inconvenience or concern with the therapeutic measures. Moderate events may cause some interference with functioning.
- Severe: events interrupt a patient's usual daily activity and may require systemic drug therapy or other treatment. Severe events are usually incapacitating.

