10.3 Study Outcomes

Stage I- Randomized Open-Label, Parallel Group

Primary Endpoints

- 1. Pharmacokinetic superiority at Day 14
 - a) Inter- and intra- patient variability: Time to attain therapeutic plasma concentrations of itraconazole (> 500 mcg/L)
 - b) Interpatient variability as calculated by co-efficient of variation

Trough (pre-morning dose) sample will be collected at Days 14 and 42. Using validated LC-MS/MS methods, blood samples will be analyzed to quantify plasma concentrations of itraconazole and hydroxyitraconazole.

Participants should arrive to the trial site having **not** taken their morning dose of study drug.

Note: site investigators are discouraged from drawing independent PK laboratories to check itraconazole levels outside of the designated timepoints (Day 14)

2. Tolerability - ability to remain on study drug at Day 42 with less than a 7-day interruption of therapy

Secondary Endpoints

- PK at day 7 plasma concentrations of itraconazole- (comparative trough, steady state plasma itraconazole concentrations of SUBA-itraconazole 65mg capsules with food to itraconazole 100mg capsules with food over 7 days)
- 2. PK at day 42 plasma concentrations of itraconazole- (comparative trough, steady state plasma itraconazole concentrations of SUBA-itraconazole 65mg capsules with food to itraconazole 100mg capsules with food over 42 days)
- 3. Efficacy: clinical outcomes (time to relief of fungal signs and symptoms) at days 14, 28, and 42
- 4. Safety- defined as: adverse events that occurred in each study arm by Day 42
- 5. Tolerability ability to remain on study drug at Days 14 & 28
- 6. Days of Hospitalization and ICU stays at Day 42
- 7. Other health economic endpoints:
 - 1. Number of unscheduled procedures (i.e., labs, scans, etc.) at Day 42
 - 2. Total number of capsules taken at Day 42
 - 3. SF-20 (QOL) assessments at Day 42

Stage II- Open-Label, Extension

Primary Endpoint

- 1. Efficacy- Free from proven or probable invasive endemic fungal infection at Day 180
- 2. Tolerability- ability to stay on study drugs at Days 43 180.

Secondary Endpoints

- 1. Safety- Adverse events that occurred in each study arm between Days 43 180 or end of therapy
- 2. Days of Hospitalization (Days 1 180) defined as days of hospitalization and ICU stays from randomization to Day 180 or end of therapy)

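### Both primary tolerability endpoints count every stop of study drug whatever its cause, so stops for worsening mycosis or for completed therapy read as intolerance, and no planned analysis separates them

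*Combined protocol and SAP*

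**What the plan says.** **Endpoints.** Section 10.3 makes tolerability a primary outcome in both stages. Stage I is "ability to remain on study drug at Day 42 with less than a 7-day interruption of therapy". Stage II is staying on drug from Day 43 to Day 180. Neither names a cause or an exception. Section 10.1 tests tolerability for superiority by chi-square, with Fisher's exact test where needed.

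**Stopping drug.** Section 6.3 says "Dose increase, reduction or cessation is permitted at the discretion of the investigator". It requires the modification to be recorded in the source document and eCRF, but does not ask for the reason. The Protocol Summary also lets therapy end before Day 180 if the Principal Investigator judges this safe; Section 4 runs therapy to Day 180 without that proviso.

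**Leaving the study.** Section 5.3.2 opens "A study subject may be discontinued from participation in the study for the following reasons" and lists any clinical AE, withdrawn consent, protocol violation and loss to follow-up. Under Section 5.3.3, "the reason for withdrawal will be documented and entered into the eCRF" when a subject is withdrawn. The source documents should also draw a "distinction between participant withdrawal from the study medication regimen and withdrawal from the study itself".

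**Adverse events.** Section 8.4.1 says "Any medical condition that is present at the time that the patient is screened should be considered as baseline and not reported as an AE", and continues "However, if it deteriorates at any time during the study, it should be recorded as an AE". The mycosis under study is not exempted. Sections 10.3 and 10.5 compare all AEs by arm, not only related ones.

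**Efficacy.** In Section 10.4 the DRC classes worsening, or lack of any resolution, as clinical failure.

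**The concern.** The protocol presents tolerability, safety and efficacy as separate properties of the two formulations. Under these definitions, a patient taken off drug because the infection worsened is a tolerability failure, an adverse event and an efficacy failure at once. A patient who recovers and stops early in Stage II is a tolerability failure although nothing went wrong.

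The trial also tests whether drug levels differ between arms, so unequal rates of progression stops cannot be ruled out. If they occur, a difference in efficacy alone could be reported as superior tolerability and fewer adverse events. If progression stops are equal, they add noise that hides a real difference in side effects.

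**Working it through.** **1. The plan's own figure.** Section 10.2 states 77% power for the Day 14 PK comparison. A two-sided Welch t-test with 40 per arm, difference 60.0, SDs 94.0 and 101.8 and alpha 0.05 gives 77.2%, so the figure reproduces. It does not bear on tolerability, for which the plan states no power and no expected rate.

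**2. How each course of events is counted.**

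| Event | Tolerability | Safety (all AEs) | DRC clinical response |
|---|---|---|---|
| Mycosis worsens, drug stopped before Day 42 | Failure | AE | Failure |
| Mycosis worsens, drug continued | Success | AE | Failure |
| No resolution, no worsening, drug continued | Success | Not an AE under the 8.4.1 sentence | Failure |
| Side effect, drug stopped before Day 42 | Failure | AE | By response |
| Stage II: stopped early because judged safe | Failure | None from the stop | Can be success |

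Rows 1, 4 and 5 all count as tolerability failures and are not told apart. Rows 2 and 3 show that an efficacy failure counts as intolerance only if drug is stopped or, in Stage I, interrupted for 7 days or more.

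**3. A false difference from efficacy alone.** Assumptions: 40 per arm (the protocol gives no allocation ratio), true intolerance 10% in each arm, and progression stops added to it. The rejection rate at two-sided 0.05 is the sum, over all pairs of failure counts (x, y) that reject, of Bin(x; 40, p1) × Bin(y; 40, p2).

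| Progression stops | Total failures p1 / p2 | Uncorrected chi-square | Fisher's exact |
|---|---|---|---|
| 5% vs 5% | 15% / 15% | 5.3% | 2.5% |
| 10% vs 5% | 20% / 15% | 9.2% | 5.5% |
| 15% vs 5% | 25% / 15% | 20.2% | 14.0% |
| 20% vs 5% | 30% / 15% | 36.6% | 28.1% |

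If the two causes act independently instead of adding, the last row becomes 1 − 0.90 × 0.80 = 28% against 1 − 0.90 × 0.95 = 14.5%. The same enumeration then gives 32% (chi-square) or 24% (Fisher).

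**4. Dilution of a real difference.** Assume true intolerance of 5% vs 25%, with independent progression stops. Retention is (1 − intolerance) × (1 − progression). Power = Φ[(|d| − 1.96·se0)/se1], where se0 uses the pooled and se1 the separate variances.

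- No progression stops: 0.95 vs 0.75; d = 0.20, se0 = 0.0798, se1 = 0.0766; power 71.5%.
- 5% in both arms: 0.9025 vs 0.7125; d = 0.19, se0 = 0.0882, se1 = 0.0856; power 58.0%.
- 10% in both arms: 0.855 vs 0.675; d = 0.18, se0 = 0.0948, se1 = 0.0926; power 47.5%.
- 10% in the better-tolerated arm, 5% in the other: 0.855 vs 0.7125; power 33.8%.
- 5% in the better-tolerated arm, 10% in the other: 0.9025 vs 0.675; power 71.0%.

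Exact enumeration of the chi-square test for the first three cases gives 76%, 60% and 48%, the same pattern.

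**The case against.** All-cause retention is a defensible, explicitly stated endpoint. In an open-label trial it has a real advantage, because it does not depend on an unblinded investigator's view of why drug was stopped. This stands, and is why the all-cause figure should be kept.

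Much of the information for a split is already collected: AE description and relatedness, DRC response at fixed visits, antifungal therapy at every visit, deaths as SAEs, and a reason for withdrawal. Section 5.3.3 could be read as requiring that reason for withdrawal from medication as well as from the study. This also stands in part: a partial split is feasible. But no reason is required for a cessation or interruption under Section 6.3, no categories are given for stopping drug, the AE items listed in Section 8.4.1 do not link an event to a stop, and no analysis by cause is planned.

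One could also read the word ability in Section 10.3 as sparing a patient who could have continued but did not need to. No rule says so, and the analyst would have to decide after seeing the data.

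Finally, every rate in the illustration is assumed. Nothing in the documents shows that progression stops by Day 42 would differ by 10 to 15 points, and with equal progression stops there is no material inflation. That is correct; the figures show what could happen, not what is expected.

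**Conclusion.** The point holds as a low-cost improvement. Section 10.3 mixes causes of stopping in both primary tolerability endpoints, and Sections 8.4.1, 10.3 and 10.5 place worsening of the study mycosis in the all-AE comparison. On the assumed rates, progression stops of 20% vs 5% alone give a significant tolerability difference in about 28 to 37% of trials, depending on the test. Equal progression stops of 5 to 10% cut the power for a true 5% vs 25% difference from 71.5% to 58.0% or 47.5%. These figures rest on 40 per arm and on rates that the documents do not give, and the direction of bias is not known in advance.

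A reader might infer more, without support in the documents:

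- That the missing lack-of-efficacy entry in Section 5.3.2 causes the mixing. The endpoint never uses that list, so adding an entry would not move one patient in the count. The list is permissive and concerns study participation, while stopping of drug falls under Section 6.3.
- That the data could not be separated afterwards. A partial split is possible; what is missing is a specified reason field for stopping drug and a planned analysis.
- That recording worsening as an AE is mandatory. The text says should, and covers deterioration, not failure to resolve.
- That all efficacy failures count as intolerance. Only those leading to a stop, or in Stage I an interruption of 7 days or more, do so.

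**What to change.** 1. In the eCRF, record the reason for every stop of study drug and every interruption of 7 days or more. Include progression or inadequate response of the mycosis, death, and therapy no longer needed among the categories.
2. In Section 10.3, keep all-cause retention for both stages. Report beside it the failures due to AEs other than the study mycosis, and state that stops because therapy was judged complete are not counted as intolerance. The Protocol Summary and Section 4 should be reconciled on whether therapy may end before Day 180, so that this rule has a fixed reference.
3. In Section 10.5, flag AEs that are worsening of the study mycosis and tabulate them separately from other AEs.

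The cost is one reason field, one AE flag and an extra table for each comparison. Treatment, visits and sample size do not change. The drawback is that an unblinded investigator assigns the reason, so the cause-specific figure should always appear with the all-cause one.

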5.3.3 Handling of Withdrawals

If a subject is withdrawn prior to the end the study, the reason for withdrawal will be documented and entered into the eCRF and if patient is willing to return to be assessed, the End of Treatment (Day 180) assessments will be completed. Documentation of withdrawal in the source documents should include a distinction between participant withdrawal from the study medication regimen and withdrawal from the study itself. In the former case case, the study medication is stopped, but the participant, if willing, continues with study visit assessments; in the latter, study medication and study visit assessments are discontinued.

5.3.4 Termination of Study

This study may be prematurely terminated by the study sponsor or the protocol team for issues related to safety, efficacy, or other reasons (please see Section 5.3.2). If early termination of the study occurs, all study participants will have all End of Treatment (Day 180) assessments completed.

6 STUDY INTERVENTION/INVESTIGATIONAL PRODUCT

6.1 Study Product Description

6.1.1 Acquisition

SUBA-itraconazole and conventional itraconazole will be provided by Mayne Pharma for use in this study. Sites should only use product that has been sourced by Mayne Pharma.

6.1.2 Formulation, Packaging, and Labeling

SUBA-itraconazole Investigator Brochure and conventional itraconazole package insert are provided as separate documents. The conventional itraconazole package insert is also located at:

http://www.janssen.com/us/sites/www janssen com usa/files/products-documents/pi-sporanoxcapsules.pdf)

SUBA-itraconazole study drug will consist of 65 mg capsules.

Conventional itraconazole will consist of 100 mg capsules.

Study drug will be packaged and labeled according to labeling instructions in the Manual of Procedures. Patients will be dispensed study drug by the site with sufficient amount of drug to last through the next study visit plus 5 days. Investigators at each site may determine if the site pharmacy may ship study drug to the participants' homes when clinic visits are not recommended or possible.

Patient initials, Study ID, and date will be recorded on dispensed study record. Documentation of dispensing, including identification of who dispensed the study drug, will be recorded in both the drug accountability log and the patient source documents.

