7.3 Follow-up

Participants will be assessed in clinic at Day 7, Day 14, Day 28 (1 month), Day 42, Day 84 (3 months) and Day 180 (6 months). In the opinion of the investigator, clinic visits may be replaced with telemedicine visits or home visits, with allowances made for blood draws at remote or commercial laboratories. Documentation in source documents should clearly define accommodations in visit locations or methods when attempting to protect participants and other patients from potential exposure and hazards related to COVID-19. The Day 7, 14 and 42 visits allow a narrow window (+/- 3 days) so that accurate PK levels can be drawn.

The Day 84 and 180 visits will allow a window of (+/- 7 days).

At each visit, blood samples will be drawn for study-specific safety and efficacy labs. In addition a quality of life questionnaire will be administered at Day 42. See Appendix A for study procedures per visit.

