7.5 Unscheduled Visit

If clinically indicated, study subjects may be asked to return to clinic to further assess safety issues, resolution of a safety issue, evaluate treatment compliance, or other reasons as determined by the investigator.

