APPENDIX A: SCHEDULE OF EVENTS

| Activities | Day 1 ^g (Baseline) | Day 7 (1 wk) +/- 3 days | Day 14 (2 wks) +/- 3 days | Day 28 (4wks) +/- 7 days | Day 42 (6 wks) +/- 3 days | Day 84 (3 mos) +/- 7 days | Day 180 (6 mos) +/- 7 days |
|---|----------------------------------|----------------------------------|------------------------------------|-----------------------------------|------------------------------------|------------------------------------|-------------------------------------|
| Informed Consent | Х | | | | | | |
| Review of Inclusion/Exclusion Criteria | × | | | | | | |
| Randomization | X | | | | | | |
| Medical History | X | | | | | | |
| Clinical Assessment: vital signs, PE ^a , & radiographs ^b ; | × | Х | Х | Х | Х | Х | × |
| Participant Administered SF-12 Quality of Life Survey | Х | | | | Х | | х |
| Tolerability | Х | | | Х | Х | | Х |
| βHCG - pregnancy test ^c | Х | | | | | | |
| Mycologic Assessment: clinical, urine and serum quantitative antigen levels^d & serum antibodies ^{e,f} | х | | х | Х | Х | Х | х |
| Serum and Urine for future use: blood, urine, saliva, sputume | X | | Х | X | Х | Х | Х |
| Plasma PK ^f | | Χ | Х | | Х | | |
| Chemistry: Creatinine, AST and Alkaline Phosphatase, Total Bilirubin ^f | Х | | Х | Х | Х | Х | х |
| Hematology: CBC with Differential ^f | X | | | X | | X | X |
| HIV Status: Documentation of any positive test; Documentation of Negative test 30 days or less prior to start of study drug. | Х | | | | | | |
| Antifungal Therapy (Pre- and during study) | Х | Х | Х | Х | Х | Х | Х |
| Dose Modifications | | | Х | X | Х | Х | |
| Study Drug Dosing & Accountability | Х | Х | Х | Х | Х | Х | Х |
| Concomitant Therapy | Х | Х | Х | Х | Х | Х | Х |
| Adverse Events | Х | Х | Х | Х | Х | Х | Х |
| Days of Hospitalization, ICU | Х | Х | Х | Х | Х | Х | Х |

^a Complete physical exam on baseline; targeted physical exams for all other visits.

b Radiograph results that were performed as standard of care to diagnose or assess the fungal infection.

^C Urine or Serum pregnancy test is acceptable.

^d Histoplasma and Coccidioides urine and serum quantitative antigen.

^e Collection of sputum, if associated with the IFI and available.

^fChemistry and hematology will be processed at the site for safety evaluations; PK samples will be sent to a central lab for processing; see Manual of Procedures for specimen handling procedures;

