gBaseline Visit: Study drug is be started on Day 1. Visit windows for Day 7, 14 and 42 will be a +/-3 day window. All other visits have a +/- 7 day window.

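### On nominal-date counting, the 5-day drug reserve is shorter than the 7-day lateness allowed for the Day 28 and Day 84 visits and can leave 2 to 3 doses uncovered

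*Combined protocol and SAP*

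**What the plan says.** Section 6.1.2 has the site dispense a "sufficient amount of drug to last through the next study visit plus 5 days". It does not define the date of the next visit for this purpose.

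The visit windows are set elsewhere. Appendix A heads the four-week column "Day 28 (4wks) +/- 7 days". Section 7.3 states "The Day 84 and 180 visits will allow a window of (+/- 7 days"). Footnote g of Appendix A gives Days 7, 14 and 42 a window of 3 days either side and adds: "All other visits have a +/- 7 day window".

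Section 6.2 sets two capsules twice daily from Day 4 in both arms, through Day 180. On leftovers, Section 6.4 says "Subjects will bring all containers and unused medication (if applicable) to each visit". The site compares returned with dispensed product, but nothing says whether leftovers go back to the patient.

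Two routes could bridge a gap. Section 6.1.2 allows home delivery: "Investigators at each site may determine if the site pharmacy may ship study drug". Section 7.5 allows an unscheduled visit, when clinically indicated, for purposes that include to "evaluate treatment compliance, or other reasons as determined by the investigator".

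The Stage I tolerability endpoint in Section 10.3 counts a patient as tolerating study drug at Day 42 if any interruption is shorter than 7 days.

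**The concern.** The reserve and the windows do not match. A site can dispense exactly what Section 6.1.2 asks, counted to the nominal date. A patient can then attend on the last day that Appendix A permits. Both have followed the protocol, yet the drug runs out first. These patients are being treated for proven or probable invasive fungal infection, and the lapse would have a purely logistical cause. Section 6.1.1 also tells sites to use only sponsor-sourced product, which limits bridging from a local pharmacy.

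What is at stake is a short, avoidable break in treatment. Both arms have the same schedule and dosing frequency, so the documents give no ground for claiming bias between them.

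**Working it through.** The plan gives no figure for uncovered doses, so there is none to reproduce.

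**Inputs.** Reserve 5 days (Section 6.1.2). Windows of 3 or 7 days either side (Section 7.3, Appendix A). Two doses a day and four capsules a day from Day 4 (Section 6.2). Assumptions: supply ends with the evening dose of the last covered day, new drug is received at the visit, and the evening dose on the visit day comes from the new supply.

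**Step 1. Last covered day against latest in-window day, counting to the nominal date.**

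| Visit | Nominal day + 5 | Latest in-window day | Shortfall |
|---|---|---|---|
| Day 7 | 12 | 7 + 3 = 10 | none |
| Day 14 | 19 | 14 + 3 = 17 | none |
| Day 28 | 33 | 28 + 7 = 35 | 2 days |
| Day 42 | 47 | 42 + 3 = 45 | none |
| Day 84 | 89 | 84 + 7 = 91 | 2 days |
| Day 180 | dosing ends | – | none |

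**Step 2. Uncovered doses.** Doses = 2 × (visit day − last covered day − 1) + m, where m is 1 if the visit comes after the morning dose time and 0 if before.

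- Visit on day +7: 2 × (35 − 33 − 1) + m = 2 to 3 doses. These are both doses on Day 34 and possibly the morning of Day 35. For Day 84 they are both doses on Day 90 and possibly the morning of Day 91.
- Visit on day +6: 2 × (34 − 33 − 1) + m = 0 to 1 dose.
- Visit on day +5 or earlier: 0.

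**Step 3. Size.** Three doses are 3 / 2 = 1.5 days, well under 7 days. A full course is 3 × 3 + 177 × 2 = 363 doses. A patient seen on day +7 at both visits could miss 6, and 6 / 363 = 1.7%.

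**Step 4. Leftovers.** On nominal counting, the smallest leftover comes from a preceding visit held 3 days late: 19 − 17 = 2 days at Day 17, or 47 − 45 = 2 days at Day 45. If this is handed back on top of a full new supply, cover reaches 33 + 2 = Day 35 or 89 + 2 = Day 91, and the gap closes.

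**Step 5. Other ways of counting.**

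- To an appointment that is kept: booked and held on Day 35, supply lasts to Day 40; on Day 91, to Day 96. No gap.
- To the end of the window: no gap.
- To an early in-window appointment that slips: booked Day 21, supply lasts to 21 + 5 = Day 26. Held on Day 35, the gap is 2 × (35 − 26 − 1) + 1 = up to 17 doses, or 17 / 2 = 8.5 days.

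**The case against.** The strongest reply is that Section 6.1.2 says visit, not nominal date. Read naturally, that is the appointment known when drug is dispensed, and a kept appointment is always covered. This stands as far as it goes: the gap is conditional, and the sentence can be read so that no gap exists. But the protocol does not settle the reading, and counting to the appointment fails if the appointment slips within the window.

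A second reply is that several things must coincide, and that there are escape routes: leftovers, home shipment, unscheduled visits, and telemedicine or home visits in place of clinic visits (Section 7.3). It is true that the documents give no frequency for visits on day +6 or +7, and that leftovers handed back on top of a full supply would close the nominal-date gap. None of these routes guarantees cover, however. Return of leftovers is not stated, and the other routes are discretionary. The Manual of Procedures may say more, but it is not among the documents.

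It is also fair that the third dose is the visit-day morning dose, which might only be taken late. That is why the result is given as a range.

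Three stronger readings are tempting, and the documents do not support them:

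- A reader might take 3 doses as the ceiling, and the tolerability endpoint as safe, however supply is counted. The Day 21 to Day 35 example shows otherwise.
- A reader might conversely infer that the tolerability endpoint is in jeopardy. That needs an early booking followed by a long slip, and nothing in the documents says how often this would occur.
- A reader might want to add a top-up after dose increases, since Section 6.3 ties dose changes to "combined drug levels (itraconazole + hydroxyitraconazole) at Day 14 and Day 42". That is a separate matter from visit windows and has not been costed here.

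**Conclusion.** The point holds in conditional form. If supply is counted to the nominal date and leftovers are not handed back on top of a full supply, the Day 28 and Day 84 visits can each leave 2 to 3 doses uncovered at day +7 and 0 to 1 at day +6. On that counting the gap cannot by itself breach the 7-day limit in the Day 42 tolerability endpoint. A longer gap is possible where supply is counted to an early appointment that slips. No effect on other endpoints and no difference between arms is claimed. The issue is minor, but it concerns continuity of treatment and the remedy is simple, so it is worth fixing as a cheap improvement.

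**What to change.** In Section 6.1.2, state that each dispensing, at the patient's current dose, must last at least through the latest in-window date of the next visit. That means through Day 35 when dispensing at Day 14 and through Day 91 when dispensing at Day 42, a reserve of at least 7 days past the nominal date for those two visits. The present 5 days can stay for the others. Because supply is then tied to the end of the window, a slipped appointment is covered too, as long as it stays in window.

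Cost at the standard dose, relative to nominal-date counting: 4 capsules × 2 days = 8 more at each of two dispensings, so 16 per patient. A full course is 3 × 6 + 177 × 4 = 726 capsules, so this adds 16 / 726 = 2.2%. For 80 patients it is at most 16 × 80 = 1,280 capsules. No visit or procedure is added.
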